Quantitative observational comparative effectiveness of quadratus lumborum block with liposomal bupivacaine (Exparel®) versus thoracic epidural analgesia in patients undergoing laparoscopic colectomy

NCT03827291

Document Date: 09/27/2022

Purpose of the Study

We believe that a quadratus lumborum block with liposomal bupivacaine(Exparel®) or a quadratus lumborum block with an admixture of bupivacaine will provide roughly equivalent analgesia and opioid use when compared with postoperative analgesia in a historical cohort that received thoracic epidural analgesia. We believe participants who receive the quadratus lumborum block will result in improved early mobilization, fewer complications such as block failure, urinary retention, and pruritis, and decreased overall pharmacy costs compared to the patients who received thoracic epidural analgesia.

Background & Significance

Laparoscopic colectomy is a surgical procedure that is primarily performed for resection of a GI malignancy. While most of the procedure is performed via laparoscopic ports in the anterior abdominal wall, the resected specimen is typically delivered through a small lower abdominal laparotomy, which results in a moderately severe burden of pain for these patients. Enhanced recovery after surgery (ERAS) protocols are aimed at improved return to function with minimal disruption in the functional capacity, and have been shown to reduce hospital length of stay, complications, and costs. One standard therapeutic component of the ERAS program at Duke for colorectal surgery is thoracic epidural analgesia (TEA), which is typically maintained for 2 days postoperatively. While TEA usually provides high-quality analgesia of the abdomen, drawbacks include technical difficulties with insertion, patchy or non-functioning block, pruritis and/or urinary retention due to epidural opioids, impairment of mobility due to leg weakness or the presence of a pump apparatus on an IV pole, and most importantly, associated hypotension which often results in the epidural local anesthetic infusion being discontinued. Alternatives to TEA include infiltrative blocks of the wall of the abdomen. The quadratus lumborum block (QLB) is a novel, ultrasound-guided infiltration technique whereby local anesthetic is deposited in the fascial plane between the quadratus lumborum and psoas major muscles at the level of L3-4.(1) Performed bilaterally, the QLB has been shown to provide a dermatomal block of the entire anterior abdominal wall. This may be the principal advantage of QLB over transversus abdominis plane (TAP) block, which is often patchy and restricted to a smaller area of the abdominal wall. In our institution, QLB is replacing TAP blockade for many abdominal procedures that have both upper and lower incisions or port sites. The QLB appears (both in the scant literature to date and in our institutional experience) to be reliable and technically simpler to perform than TAP blocks, as the needle is not moved once the fascial plane is breached. We wish to compare the effectiveness of QL blocks for postoperative analgesia in this population with a historical cohort that received thoracic epidural analgesia. Based on our experience, we believe that infiltrating this space with an admixture of bupivacaine and liposomal bupivacaine will result in excellent pain relief for an extended duration of time. Liposomal bupivacaine (Exparel®) is a slow-release, long-acting form of bupivacaine that has been shown to provide extended duration of analgesia and opioid sparing

in a number of surgical settings. (2, 3) Liposomal bupivacaine is FDA approved for surgical infiltration, field blocks, fascial plane blocks of the abdomen, dental blocks, and interscalene brachial plexus blocks. A number of new abdominal wall block techniques have been developed over the last several years, and following some initial confusion related to the wording of the label, the FDA issued a clarification letter that stated that truncal fascial plane blocks such as the transversus abdominis plane (TAP) block are an on-label use of the medication (see attached clarification letter). The quadratus lumborum (QL) block is a type of TAP block, wherein local anesthetic is infiltrated into the fascial plane between muscles of the lateral abdominal wall.

Design & Procedures

This is a single center, observational prospective and retrospective cohort study.

Prospective: On the day of surgery, subjects will receive a QLB in the preoperative holding area as follows:

Subjects will be positioned in the right lateral decubitus position, and will be attached to standard ASA monitors (pulse oximetry, EKG, non-invasive blood pressure). Oxygen 5 L/min will be supplied via a face mask. Sedation/analgesia with midazolam 1- 2 mg IV and fentanyl 25- 100 mcg IV will be administered.

After appropriate skin preparation and draping, a 60 mm, 2-5 MHz curvilinear ultrasound transducer will be placed on the skin over the intercristal line (approximately L3/4 disc space) on the midline of the back. The transducer will be translated laterally to the left until the quadratus lumborum and psoas major muscles are identified. The transducer will then be rotated until the quadratus muscle is seen in its long axis, just below its attachment on the 12th rib.

A 21 gauge, 10 cm echogenic block needle (Pajunk Sonoplex, Norcross, GA) will then be inserted from the inferior aspect of the transducer and advanced until the tip is visualized in the fascial plane between the QL and psoas major muscles. Following negative aspiration for blood, 30 ml of injectate will be slowly administered with intermittent aspiration. Each 30 ml aliquot will contain 10 ml of liposomal bupivacaine (133 mg) and 20 ml of 0.25% bupivacaine (50 mg). The block will then be repeated on the right side.

Following the block, subjects will proceed to the operating room where they will undergo a standard general anesthetic with endotracheal intubation (desflurane or isoflurane in a mixture of air/oxygen). The dosing of intraoperative opioids will be left to the discretion of the attending anesthesiologist in the room.

In the Post-Anesthesia Care Unit (PACU) and on the postoperative floor, subjects will have access to oxycodone 5-15 mg PO q3h prn for rescue analgesia (the primary outcome measure). In the PACU, patients will also have access to intravenous hydromorphone if the oral opioid

provides inadequate relief. Finally, subjects may receive a standard multimodal analgesia regimen consisting of:

- Acetaminophen 975 mg PO q6h (beginning in preop holding)
- Gabapentin 600 mg PO once in holding, then 100 mg PO tid thereafter
- Ketorolac 15 mg IV prior to skin closure

While this standard regimen is expected, it may vary per clinical care team judgement and/or preference. Any alterations in this standard regimen will not be considered a protocol deviation.

Assessments

Patient assessments will be performed or recorded by a research assistant twice daily (unless otherwise specified). Assessments made after discharge will be recorded by subjects who will be provided with a diary to document the outcomes. Outcomes to be measured include:

Opioid consumption. Cumulative opioid consumption over 48 hours is the primary outcome measure. Data will be drawn from PACU records and from the nursing medication records on a twice-daily basis. Post discharge opioid use will be tracked in the take-home patient diary. The patient will be called at 7 days after surgery to collect.

NRS-11. The 11-point Numeric Rating Scale (0-10) will be used as a secondary outcome measure. Two measures will be taken with each assessment, one at rest and one with coughing. These will be conducted preoperatively, 30 minutes after arrival to PACU, and at time points 8 hrs., 24 hrs., 36 hrs. 48 hrs, 72 hrs, 96 hrs., 120 hrs., 144 hrs. and 168 hrs.

Block success and adverse events. Presence of demonstrable sensory block over 4 points on the abdomen (one in each of the 4 quadrants), as tested by response to pinprick. Subjects will be asked to report whether the stimulus feels “sharp” or “dull”, indicating block failure and success respectively. This will be done at the time of pain assessment (30 minutes after arrival to PACU, and at time points 8 hrs., 24 hrs., 36 hrs. and 48 hrs. and 72 hrs.). Subjects will be evaluated for potential adverse events related to the block including evidence of hematoma, infection, unexpected sensory or motor deficit, local anesthetic systemic toxicity, as well as transient weakness of the hip flexor muscles (a known possible side-effect of QL block).

Satisfaction with postoperative pain control. Overall subject satisfaction with pain control will be recorded on postoperative day 0 and 1 (11-point scale: 10=highly satisfied, 0=completely unsatisfied)

Hospital length of stay. Measured both by raw length of stay and by time to achieving “discharge readiness”, defined by the presence of 3 criteria: a pain score of 3 or less with ambulation, no opioids required in the preceding 6 hours, and the ability to perform self-care (go to the toilet, dress, and shower).

Incidence of opioid-related adverse events. Incidence of nausea, vomiting, ileus, constipation, orthostasis, pruritis, urinary retention, respiratory depression

Time to first mobilization. Measured from time of arrival in PACU (time zero)

Cost. Hospital costs including pharmacy-related costs, costs due to opioid-related adverse events, the cost associated with nursing interventions and drugs to treat opioid-related adverse events, and overall hospital admission costs will be calculated.

Sleep Quality. Two measures will be taken for sleep quality assessment. How much did pain interfere with falling asleep (0= no interference, 10= completely interferes). How much did pain interfere with staying asleep (0= no interference, 10= completely interferes). Measures will be taken once daily from POD 1 to POD 7 (approximately 168hrs. after surgery). If the subject is sleeping at the time assessment collection is due, the subject will not be disturbed to collect the assessments, and this will not be considered a protocol deviation.

Historical data of 30 patients that meet inclusion criteria and meet no exclusion criteria, will be collected and for the retrospective group. The anesthesia statisticians will evaluate the following data from the patient's electronic medical record if available, including but not limited to hospital notes, anesthesia notes, medical history, medications, pain service notes, and flowsheets from admission to discharge. Electronic medical records will be used to assess the following items to compare to the prospective cohort.

Opioid consumption. Cumulative opioid consumption at 24hours, 48 hours and 72 hours. 48 hours is the primary outcome measure. Data will be drawn from PACU records and from the nursing medication records.

NRS-11. The 11-point Numeric Rating Scale (0-10) will be used as a secondary outcome measure. These will be collected from the preoperative assessment record, 30 minutes after arrival to PACU, and at time points 8 hrs., 24 hrs., 36 hrs. 48 hrs. and 72 hrs.

Thoracic epidural success and adverse events. Evidence of epidural block success/failure (as described in the anesthesia record and in daily Inpatient Pain Service notes). This will be done at the time of pain assessment (30 minutes after arrival to PACU, and at time points 8 hr, 24 hr, 36 hr and, 48 hr and 72 hr). Subject data will be collected for potential adverse events related to the epidural including evidence of hypotension, urinary retention, inability to ambulate per physical therapy. (known possible side-effect of thoracic epidural approach).

Hospital length of stay. Measured both by raw length of stay and by time to achieving "discharge readiness", defined by the presence of 3 criteria: a pain score of 3 or less with ambulation, no opioids required in the preceding 6 hours, and the ability to perform self-care (go to the toilet, dress, and shower).

Incidence of opioid-related adverse events. Incidence of nausea, vomiting, ileus, constipation, orthostasis, pruritis, urinary retention, respiratory depression

Time to first mobilization. Measured from time of arrival in PACU (time zero)

Cost. Hospital costs including pharmacy-related costs, costs due to opioid-related adverse events, the cost associated with nursing interventions and drugs to treat opioid-related adverse events, and overall hospital admission costs will be calculated.

Selection of Subjects

Criteria for inclusion in Prospective cohort:

- Patients scheduled for elective, laparoscopic colonic resection by one of three surgeons: Drs. [name], [name] or [name]. These surgeons perform this procedure in the same manner
- Age 18-85 years
- American Society of Anesthesiologists (ASA) Physical Class I-III
- BMI 18-35 kg/m²

Criteria for exclusion in Prospective Cohort:

- Inability to consent
- Inability to speak English
- Pregnancy
- Emergency surgery
- Contraindications to regional blockade: coagulopathy or bleeding diathesis, local infection, allergy to local anesthetics
- Allergies/intolerances/contraindications to any of the multimodal agents (acetaminophen, gabapentin, ketorolac)
- Daily opioid equivalent use of 30 mg of morphine or greater at time of consent
- History of drug or alcohol abuse
- Uncontrolled anxiety, schizophrenia or other psychiatric disorder that, in the opinion of the investigator, may interfere with the study assessments of compliance.

Criteria for inclusion in Retrospective cohort:

- Patients that have had a laparoscopic colonic resection in the past year by Drs. [name], [name] or [name] and received thoracic epidural analgesia.
- Thoracic epidural analgesia must be placed in preoperatively, must be sited between levels T8 and T12, and must be started while the case is going- i.e. not started in PACU.
- Age 18- 85 at the time of the procedure.
- American Society fo Anesthesiologists (ASA) Physical class between I- III.
- BMI 18- 35 kg/m².

- Received the standard multimodal medication regimen for pain as outlined in the ERAS protocol for colorectal surgery

Criteria for exclusion in Retrospective cohort:

- Emergency surgery
- Daily opioid equivalent use of 30 mg of morphine or greater at time of consent.
- History of drug or alcohol abuse.
- Uncontrolled anxiety, schizophrenia or other psychiatric disorder.

Risk/Benefit Assessment

Risks of the study intervention relate to those associated with the quadratus lumborum block. These include routine risks of block procedures including bleeding, infection, nerve damage, local anesthetic systemic toxicity, as well as transient weakness of the hip flexor muscles (a known possible side-effect of QL block).

If subjects receive the quadratus lumborum block, they may experience improved pain control and/or reduced side effects compared to the epidural pain relief option, but it is not known yet whether this will be the case.

Data Analysis & Statistical Considerations

We will use descriptive statistics (mean (SD) or frequency (%)) and group comparisons via Wilcoxon rank sum or fisher exact tests to measure differences between cohorts in opioid consumption, pain scores with rest and activity, and other secondary outcome measures.

Sample Size Justification

A difference in opioid consumption less than 20% would be considered non-inferior. Based on typical postoperative opioid consumption following laparoscopic colectomy (20mg +/- 5.2 mg), a total of 54 subjects (27 in each group) would be required to reject the null hypothesis that QL blockade is inferior in the first 48 hours with the study intervention, given an alpha of 0.05 and a power of 0.8. We plan on recruiting 45 subjects to account for dropout.

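### The purpose predicts roughly equivalent analgesia, but pain has no margin and only a difference test, so a non-significant result cannot show equivalence and could be misread as doing so

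*Combined protocol and SAP*

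**What the plan says.** The Purpose of the Study states a belief in two parts, analgesia and opioid use: QLB "will provide roughly equivalent analgesia and opioid use" relative to historical patients given thoracic epidural analgesia. The Assessments section makes 48-hour cumulative opioid consumption primary and the 11-point pain score secondary.

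The Sample Size Justification gives the only margin, and it concerns opioid use: "A difference in opioid consumption less than 20% would be considered non-inferior". The only formal hypothesis is there too. The sample is chosen "to reject the null hypothesis that QL blockade is inferior in the first 48 hours", "given an alpha of 0.05 and a power of 0.8".

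Data Analysis & Statistical Considerations gives one method for all outcomes, descriptive statistics plus "group comparisons via Wilcoxon rank sum or fisher exact tests to measure differences between cohorts". Opioid consumption and pain, at rest and on activity, are both named as outcomes to be compared this way. Pain has no margin, no assumed SD, no key time point and no confidence-interval rule. The documents do not say how a non-significant pain comparison will be interpreted.

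**The concern.** A rank-sum test asks whether the data contradict equality. A large p-value may mean that the cohorts are alike, or that the sample was too small to separate them, and the test cannot tell which. The analysis as written therefore offers no route to the analgesia half of the stated belief.

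Opioid use cannot stand in for pain. Rescue oxycodone is given as needed, so patients in one cohort may take a similar amount and hurt more. At stake is a report that combines similar opioid use with no significant difference in pain and calls the result equivalent analgesia, while the data remain compatible with meaningfully worse pain under QLB.

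**Working it through.** **1. The plan's own figure.** Inputs from the Sample Size Justification: mean 20 mg, SD 5.2 mg (reading the plus-minus figure as an SD), margin 20% × 20 = 4 mg, alpha 0.05, power 0.8.

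n per group = 2 × [5.2 × (1.960 + 0.842) / 4]² = 26.5, so 27 per group and 54 in total. This matches "a total of 54 subjects (27 in each group) would be required". It corresponds to two-sided 0.05 (one-sided 0.025); one-sided 0.05 would give 21 per group. The calculation covers opioid use only.

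**2. Precision for pain.** The documents give no pain SD, so SD 1.5 to 3 is an assumption. Two sample sizes are shown: 27/27 from the calculation above, and 45/30. The second takes the planned 45 recruits as the prospective arm, which the plan does not state, against the 30 historical patients.

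- 95% CI half-width = 1.96 × SD × √(1/n₁ + 1/n₂). The root is 0.2722 at 27/27 and 0.2357 at 45/30.
- Probability that one two-sided 0.05 test is non-significant when QLB is truly 1 point worse ≈ Φ(1.96 − 1/SE), with SE = SD × root. Example: SD 2 at 27/27 gives SE = 0.544, 1/SE = 1.84, and Φ(0.12) ≈ 0.55.

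| Assumed SD | Half-width 27/27 | Missed 27/27 | Half-width 45/30 | Missed 45/30 |
|---|---|---|---|---|
| 1.5 | 0.80 | 31% | 0.69 | 19% |
| 2 | 1.07 | 55% | 0.92 | 44% |
| 2.5 | 1.33 | 69% | 1.15 | 60% |
| 3 | 1.60 | 77% | 1.39 | 71% |

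A simulation of the rank-sum test itself, on scores rounded to 0-10 with an assumed epidural mean of 4, gives slightly higher miss rates: 59% (SD 2) and 72% (SD 2.5) at 27/27, and 48% and 64% at 45/30.

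**3. What a margin would allow.** Suppose there is no true difference and both 95% limits must lie within the margin.

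- Margin of 1 point, SD 2: the chance of showing equivalence is nil at 27/27, because the half-width of 1.07 already exceeds 1, and 13% at 45/30. Non-inferiority alone (one-sided 0.025, 80% power) would need 63 per group.
- Margin of 2 points, SD 2: the chance is 91% at 27/27 and 98% at 45/30.

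**4. The opioid endpoint.** With the plan's own SD, the half-width at 27/27 is 1.96 × 5.2 × 0.2722 = 2.77 mg. Non-inferiority at 4 mg requires an observed excess below 4 − 2.77 = 1.23 mg. A mean-based difference test stays non-significant up to 2.77 mg. An observed excess between 1.23 and 2.77 mg would thus be non-significant without meeting the margin. The rank-sum test need not turn at exactly these points, but it answers the same wrong question. Equivalence within ±4 mg, judged by a 95% interval with 80% power, would need 36 per group.

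**The case against.** The Purpose is worded as a belief and says only *roughly*. Pain is openly secondary in a small observational study, and the one formal hypothesis concerns opioid use. Asking for a margin on a secondary outcome can look like preference, and rewording the Purpose would close the gap as well. That stands in part: this is a mismatch between an aim and its analysis, not a failure of the sample size calculation, and rewording is an acceptable remedy.

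A reader might infer that the plan will treat a non-significant pain test as proof of equivalence. The documents do not support that. They say the tests measure differences and state no rule for interpreting a null result. The supportable statement is that such a result could be misread.

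A reader might also infer that the study is too small to judge analgesia. That is not established either, because the documents give neither a pain SD nor a margin. At SD 1.5 the miss rates fall to 19-31%, and at SD 2 with a 2-point margin 27 per group is ample. The miss rates are also per test. The cohorts share several postoperative time points, so non-significance at all of them is less likely than at any one.

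Finally, it is tempting to treat opioid use as the safe part of the plan and retreat to it. It is assigned the same difference test, with no rule linking an interval to its margin.

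**Conclusion.** The concern holds as a gap in the planned inference. The plan predicts roughly equivalent analgesia, sets no pain margin, and provides only a test of difference, which cannot support that prediction. This part needs no outside figure.

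The numerical size is conditional. It rests on the assumed pain SD, a 1-point worsening chosen for illustration, and, for 45/30, an uncertain reading of the recruitment target. With SD 2-3 the 95% interval extends about 0.9-1.4 points either side at 45/30 and 1.1-1.6 at 27/27; at SD 1.5, about 0.7-0.8. The point should be settled before analysis. It does not affect the choice of primary endpoint, but it does reach the primary analysis, where the 20% margin is stated without a test that uses it.

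**What to change.** Keep pain secondary and add the following to the analysis section:

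- **Estimate.** Report the QLB-TEA difference in pain score (Hodges-Lehmann or mean) with a 95% confidence interval at named time points common to both cohorts, for example 24 h and 48 h, and state that both must meet the criterion.
- **Measure.** Use a pain measure available in both cohorts. The prospective scores are taken at rest and with coughing, but the retrospective list does not make that split and depends on what the record holds. A resting score should not be assumed.
- **Margin.** The investigators set it in advance and justify it.
- **Wording rule.** Allow *non-inferior analgesia* only if the upper limit is below the margin, and *equivalent* only if both limits lie within plus or minus the margin. Otherwise describe the pain results without an equivalence claim. Alternatively, reword the Purpose so that the pain aim is descriptive.
- **Primary endpoint.** Apply the same interval rule to 48-hour opioid use, and state whether the 20% margin is a fixed 4 mg or a fraction of the epidural cohort's mean. Meeting it on one side supports non-inferior, not equivalent, opioid use.

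The cost is a short addition to the analysis text, a check of which pain scores the historical records contain, and the work of justifying a margin. The primary endpoint and study procedures do not change. The real downside is that the analgesia claim may not be reachable at this sample size, and requiring both time points makes it harder still.

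### Post-discharge opioid use is recorded by diary in the QLB cohort but has no named source in the TEA cohort, so TEA patients discharged before a window closes may be under-counted

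*Combined protocol and SAP*

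**What the plan says.** For the prospective QLB cohort, the Opioid consumption item under Assessments states: "Cumulative opioid consumption over 48 hours is the primary outcome measure". The source is given next: "Data will be drawn from PACU records and from the nursing medication records on a twice-daily basis". It then adds: "Post discharge opioid use will be tracked in the take-home patient diary". A telephone call 7 days after surgery is used for collection.

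For the historical TEA cohort, the corresponding item in the historical-data part of the same section reads: "Cumulative opioid consumption at 24hours, 48 hours and 72 hours. 48 hours is the primary outcome measure". Its source is: "Data will be drawn from PACU records and from the nursing medication records". The surrounding chart review covers "hospital notes, anesthesia notes, medical history, medications, pain service notes, and flowsheets from admission to discharge". That list is described as not exhaustive, but the opioid item names its own two sources, and both are inpatient records. No diary, call or other post-discharge source is named for TEA.

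The historical items are collected for comparison with the prospective cohort. Data Analysis & Statistical Considerations specifies Wilcoxon rank sum and Fisher exact tests. It has no rule for patients discharged before 48 or 72 h. Length of stay is an outcome in both cohorts, but no expected value is given for either.

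**The concern.** A cumulative total over a fixed window is comparable between cohorts only if both are observed for the whole window. Take two patients who leave hospital at the same hour, before the window closes. On the sources named, the QLB patient's later doses are recorded in a diary, while the TEA patient's later doses are recorded nowhere. If the TEA total is simply the sum of charted doses, those later doses are counted as zero. This is differential measurement between the cohorts being compared, not merely a missing detail.

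The primary is framed as non-inferiority on opioid use, with QLB as the new treatment. Under-counting TEA makes QLB look worse by comparison, so what is at stake is lost power and a possible false failure to show non-inferiority. A second consequence does not depend on TEA discharges: for any QLB patient who leaves before 48 h, the primary endpoint may combine charted administrations with self-report.

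**Working it through.** **Inputs from Sample Size Justification.** Mean 20 mg, SD 5.2 mg, margin 20%, alpha 0.05, power 0.8, 27 per group. The margin in mg is 0.20 × 20 = 4 mg.

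**Reproducing the plan's figure.** For non-inferiority of two means with no true difference:

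n per group = 2 × (z_alpha + z_power)² × SD² / margin²

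With one-sided 0.025 this is 2 × (1.960 + 0.842)² × 5.2² / 4² = 26.5, rounded up to 27 per group, 54 in total. The stated figure reproduces. With one-sided 0.05 the result is 21 per group, 42 in total, which does not match. Power at 27 per group is Φ(4 / (5.2 × √(2/27)) − 1.960) = Φ(2.826 − 1.960) = 0.807.

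**Illustration for the 48 h primary.** The documents give neither the share of patients discharged early nor the time of discharge, so both are assumed here:

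- The 20 mg is spread evenly over 48 h, which is 20/48 = 0.417 mg per hour.
- A fraction f of TEA patients leave 12 h before the window closes. Each loses 12 × 0.417 = 5.0 mg from the total.
- The cohorts are truly equal, QLB capture is complete (diary doses counted), and the SD and the 4 mg margin are unchanged.

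Bias in QLB minus TEA = f × 5.0 mg. Power = Φ((4 − bias) / (5.2 × √(2/27)) − 1.960).

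| TEA patients leaving 12 h early | Bias, mg | Share of margin | Power, 27 per group |
|---|---|---|---|
| 0% | 0 | 0% | 0.807 |
| 5% | 0.25 | 6% | 0.755 |
| 10% | 0.50 | 13% | 0.696 |
| 25% | 1.25 | 31% | 0.493 |

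These powers are for a comparison of means, as in the plan's own sample-size calculation. The planned test is a Wilcoxon rank sum, so they show the order of the effect and are not exact predictions.

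**Which rows are plausible at 48 h.** Background & Significance describes "thoracic epidural analgesia (TEA), which is typically maintained for 2 days postoperatively". Discharge before 48 h should therefore be uncommon in TEA, and the 0% row is plausible. It is not guaranteed: the same section says that hypotension often leads to the infusion being stopped, and two days is described as typical, not as a minimum.

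**At 72 h.** An epidural ending at about 48 h leaves roughly 24 h in which a TEA patient could go home before the window closes, within an enhanced-recovery program described as shortening stay. Truncation is likely, but it cannot be sized. The plan gives no 72 h margin, so no ratio to a margin is calculated.

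**The case against.** The strongest reply is that the primary is probably little affected. A two-day epidural keeps most TEA patients in hospital to about 48 h, and if none leaves earlier the bias on the primary is zero. This stands.

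A second reply is that the plan does not say that diary doses enter the 48 h total. The QLB item first names the same two inpatient sources as the TEA item. The diary sentence comes after them and could describe follow-up beyond the primary window. Nor does the plan say that a discharged TEA patient scores zero afterwards; the value could be treated as missing. Both points stand as ambiguities, and they are why the plan needs a rule. If diary doses were excluded, capture would be equal, but totals would then be cut at discharge in both cohorts, which favours whichever cohort leaves earlier.

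Third, incomplete diaries would lower the QLB totals and offset part of the bias. This is true, by an unknown amount.

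Three stronger readings are tempting and not supported:

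- A reader might infer that the 72 h totals are certain to be truncated. No length of stay is given, so this is likely but not established. A 72 h opioid total is listed only for TEA ("Cumulative opioid consumption at 24hours, 48 hours and 72 hours"); the QLB item lists none, so a 72 h comparison is implied by the stated purpose of the historical data.
- A reader might set a 72 h bias against the 4 mg margin. That margin belongs to the sample-size statement for the first 48 hours.
- A reader might infer that the asymmetry could produce a false claim of non-inferiority. Under-counting TEA works the other way.

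**Conclusion.** The asymmetry in the named sources is real, and the plan has no rule to handle it. It is likely to matter for any 72 h comparison between cohorts. For the 48 h primary it matters only to the extent that patients leave before 48 h. Its size cannot be determined from the documents. Under the stated assumptions, 5-25% of TEA patients leaving 12 h early would shift the comparison by 0.25-1.25 mg against QLB and reduce power from 0.81 to between 0.76 and 0.49. With no early discharge there is no shift. The direction rests on diary doses being counted for QLB and missing TEA doses being counted as zero. On that reading the risk is a false failure of non-inferiority, not a false success. The point deserves correction because it touches the primary endpoint, the stated sample size leaves little spare power (0.807), and the remedy is cheap.

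**What to change.** 1. State whether post-discharge diary doses count toward the 48 h total, and how a patient in either cohort who is discharged before a time point is scored.
2. Report the number discharged before 48 h and before 72 h in each cohort. Length of stay is already collected in both.
3. Add a 48 h sensitivity analysis that uses the same inpatient record sources in both cohorts and excludes post-discharge diary doses. Note beside it that such totals can favour the cohort discharged earlier.
4. Label any 72 h comparison between cohorts as descriptive, and state that post-discharge capture is unequal.

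Three alternatives should be avoided. Replacing the primary with inpatient-only totals would discard valid QLB doses and could favour QLB if those patients leave sooner. Restricting the 72 h comparison to patients still in hospital conditions on a post-treatment outcome and selects slower recoverers. Opioid use per inpatient hour mixes consumption with length of stay.

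The cost is a few sentences, one extra table and a more limited 72 h claim. No new data collection is needed.
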